5. TREATMENT ALLOCATIONS

5.1. Experimental Arm – Strain or shear wave RTE in conjunction with Ultrasound-guided Fine Needle Aspiration cytology

RTE is a technology that can be used at the same time as the routine ultrasound examination. RTE may help differentiate benign from malignant nodules based on the compression characteristics of the two (as benign nodules are less firm than malignant ones). It would also help identify the best part within the nodule to obtain an FNA. This may help reduce sampling errors and also improve the accuracy of the first FNA, by guiding the radiologist to the nodule that is most likely to be malignant. RTE may also help guide the radiologist to the parts of large heterogeneous nodules that are most likely to contain malignant cells. This may also improve the nodule diagnostic rate (i.e. reduce the non-diagnostic rate).

All repeat FNAC must be undertaken using the same ultrasound technique as the first one specified by the randomisation and ideally by the same RTE-accredited radiologist.

5.1.1 Training and accreditation for RTE

Radiologists and senior sonographers trained and accredited in RTE and US-FNAC of the thyroid will deliver the intervention.

As elastography is not yet commonly used in the UK, and many radiologists do not have experience of this technique, all participating radiologists and any senior sonographers delivering the intervention, will be required to attend a training and accreditation module developed for the ElaTION trial.

STEP 1: Participating radiologists will need to submit an audit of the FNAC results of 20 consecutive FNACs that they have undertaken in the last 18 months, and the total number of US FNACs undertaken in the last year.

STEP 2: Participating radiologists will attend a workshop on RTE.

STEP 3: Following the workshop, the radiologist will use RTE in conjunction with normal ultrasound on 15 patients in their normal radiology lists in their trusts to gain experience. A logbook of cases will be required with outcome of the FNAC result.

STEP 4: Do a 'hot case' accreditation – where the radiologist will perform RTE ultrasound on one patient attending a radiology list and indicate which nodule they would sample. Following successful completion of the programme, accreditation in RTE will be awarded.

STEP 5: The scans of the first 5 RTE cases done by each radiologist will be reviewed by the Trial Central Radiology Panel.

STEP 6: Online elastography community: as part of radiologist's ongoing training, complex cases can be circulated via email for further discussion by all the radiologists. The email address for circulation of cases is [contact]. Once the radiologists have completed the accreditation process they will be added onto the list by the ElaTION trial coordinator.

5.2. Control Arm – Conventional Ultrasound-guided Fine Needle Aspiration cytology

Conventional grey scale and colour Doppler US-guided FNAC for all the FNACs required until a definitive diagnosis is obtained.

All repeat FNAC must be undertaken using the same ultrasound technique as the first one specified by the randomisation and ideally by the same RTE-accredited radiologist.

5.3. Other management at discretion of local doctors

Apart from the trial treatments allocated at randomisation, all other aspects of patient management are at the discretion of the local doctors, with no other special treatments or investigations and no additional follow-up visits.

5.4. Withdrawal from randomised allocation or protocol violation

Patients may withdraw at any time during the trial if they choose not to continue, or if their clinical team feel that continued participation in the trial is inappropriate.

There are different types of withdrawal:

- The patient does not want to attend trial specific follow-up visits, but has agreed to be followed-up according to standard practice (i.e. has agreed that follow-up data can be collected at standard clinic visits)
- The patient is not willing to be followed up for trial purposes at any further visits (i.e. has agreed that any data collected prior to the withdrawal of consent can be used in the trial final analysis)

Full details of the reason(s) for withdrawal should be recorded on the Case Report Forms (CRFs) if healthcare professional-initiated, otherwise a simple statement reflecting patient preference will suffice. Patients who withdraw from trial treatment, but continue with on-going follow-up and data collection should be followed-up in accordance with the protocol.

5.5. Blood and tissue sample collection- ElaTION Collect (Translational research)

Blood samples – 20 ml EDTA and 20ml cf-DNA of blood sample, to be used in translational research, will be collected prior to the first FNAC if the patient has consented for this at trial entry. The blood sample should be labelled with the trial number and patient initials. If missed prior to the first FNAC, blood samples can still be collected up until the time of surgery; the blood sample tubes should be annotated with the date collected. The tube should be sealed and sent in the blood box provided to the ElaTION COLLECT laboratory at InHANSE. For those patients who undergo surgery, follow up bloods at 3 and 12 months post-surgery will also be requested, further bloods will be requested from the time of recurrence if during the 12 month follow up period.

FNAC samples and FFPE blocks – Provided the patient has not withheld consent for tissue to be donated and used for research, one slide from FNAC and tissue from the time of surgery (if surgery occurs), should be sent to the ElaTION COLLECT Sample Lab at InHANSE

For each patient undergoing surgery, two FFPE block of normal tissue and two FFPE blocks of tumour tissue should be sent. In addition, should a neck dissection be performed, two blocks of normal lymph node and, if applicable, two blocks of involved lymph nodes should be sent. These samples will be used for translational research.

Quality assurance samples – These are separate to the translational tissue collection samples. To ensure quality assurance, all Thy 3, 4 and 5 FNACs, a random sample of 5% of all Thy 1 & 2 FNACs and all thyroidectomy histological samples will undergo central review by the ElaTION cyto/histopathologists. These will be requested by the ElaTION Trial Office and are to be sent to the Central Review Team directly at The Pennine Acute Hospitals NHS Trust.

Full details for the preparation and sending of blood and tissue samples are provided in the appendices. For quality assurance of tissue samples please refer to page 15.

5.6. Compatibility with other studies

Patients can be in both ElaTION and other non-interventional trials.

A patient can be part of both ElaTION and another interventional trial, provided the other trial does not affect i) the decision to do a US-FNAC and ii) the decision to undertake surgery based on the FNAC result. Please contact the ElaTION trial office to discuss these patients' eligibility prior to entry into ElaTION or other studies.

6. SAFETY MONITORING PROCEDURES

The collection and reporting of data on adverse events and serious adverse events will be in accordance with ICH GCP and the Research Governance Framework 2005. It is imperative that all investigators have a thorough understanding of anticipated adverse events and the reporting process of these events.

There are no Investigational Medicinal Products (IMPs) used as part of this trial. As all of the surgical techniques being tested in this trial are used as standard practice there are no (serious) adverse events which would be anticipated as a unique consequence of participation in the trial. Any trial-related serious adverse events (SAEs) which require immediate reporting will be reported on a trial-specific SAE form and will follow the procedure and timeframes outlined in this section of the protocol.

Other outcomes, which may also be considered safety outcomes, but which are anticipated outcomes for this group of patients, will be captured on the routine follow-up CRFs (30-day and 6-month Post-Operative CRFs), these include:

- Vocal cord palsy
- Temporary or permanent hypocalcaemia
- Haematoma
- Infection
- Re-operation due to surgical complications

6.1. General Definitions

Adverse Events (AEs)

An AE is any untoward medical occurrence in a subject to whom a research treatment or procedure has been administered, including occurrences which are not necessarily caused by or related to that treatment or procedure.

Adverse Reactions (ARs)

An AR is any untoward and unintended response in a subject which is caused by or related to a research treatment or procedure.

Serious Adverse Events (SAEs)

An SAE is an untoward event which:

- Results in death
- Immediately threatens the life of participant*
- Results in hospitalisation or a longer than anticipated stay in hospital
- Results in a persistent or significant disability
- Results in any congenital anomaly or birth defect in any pregnancy

*Life-threatening in the definition of a serious adverse event or serious adverse reaction refers to an event in which the subject was at risk of death at the time of the event. It does not refer to an event which hypothetically might have caused death if it were more severe. Important adverse events/reactions that are not immediately life-threatening or do not result in death or hospitalisation, but may jeopardise the subject or may require intervention to prevent one of the other outcomes listed in the definition above, should also be considered serious.

Non-serious adverse events/reactions

Most AEs that occur in this trial, whether they are serious or not, will be 'expected'. Non-serious adverse events/reactions will be recorded in the medical records and routine follow-up CRFs.

Expected SAEs

The following are SAEs that could be reasonably expected for this group of patients during the course of the trial:

- Recognised side-effects of the treatment or disease, or an event which is secondary to those recognised effects.
- Hospitalisations for routine treatment or monitoring of the studied indication, not associated with any deterioration in condition
- Hospitalisations for treatment, which was elective or pre-planned, for a pre-existing condition that is unrelated to the indication under study, and did not worsen
- Admission to a hospital or other institution for general care, not associated with any deterioration in condition
- Treatment on an emergency, outpatient basis for an event not fulfilling any of the definitions of serious given above and not resulting in hospital admission

For the purposes of this trial these expected SAEs do **NOT** require reporting on an SAE form. These events should continue to be recorded in the source data according to local practice and be included on the routine follow-up CRFs (the 30-Day Post-Operative Assessment CRF and the 6-Month Post-Operative Assessment CRF)

Disease related morbidity and routine treatment or monitoring of a pre-existing condition that has not worsened will **NOT** be considered as SAEs and should **NOT** be reported to the Trial Office.

6.2. Serious Adverse Events for expedited reporting

SAEs occurring within 1 week (and not listed as 'expected' as defined above) will always be reportable to the ELaTION Trial Office on an SAE form. The assessment of relatedness to the trial intervention is a clinical decision and will be based on all available information at the time.

SAEs outside of this timeframe can also be reported if it is the opinion of the Investigator that there is a possible causal relationship to another aspect of the trial. An assessment of relatedness and expectedness will also be undertaken by the Chief Investigator (or delegated deputy).

All SAEs will be followed-up until the event has resolved or a decision has been taken for no further follow-up.

6.3. Reporting SAEs

All SAEs must be recorded on the SAE Form and faxed to the ELaTION Trial Office on [name] within 24 hours of the research staff becoming aware of the event.

The Principal Investigator (or other nominated clinician) has to assign seriousness and causality to the SAE before reporting.

For each SAE, the following information will be collected:

- full details in medical terms with a diagnosis, if possible
- its duration (start and end dates; times, if applicable)
- action taken
- outcome
- causality, in the opinion of the investigator*

*Assessment of causality must be made by a doctor. If a doctor is unavailable, initial reports without causality assessment should be submitted to the BCTU by a healthcare professional within 24 hours, but must be followed up by medical assessment as soon as possible thereafter, ideally within the following 24 hours.

The local investigator and others responsible for patient care should institute any supplementary investigations of SAEs based on their clinical judgement of the likely causative factors and provide further follow-up information as soon as available.

6.4. Notification of deaths

All deaths will be reported to the BCTU on the SAE Form (Appendix K) irrespective of whether the death is related to disease progression or an unrelated event. If a participant dies, any postmortem findings must be provided to the BCTU with the SAE form. The BCTU will report all deaths to the DMEC for continuous safety review.

6.5. Pharmacovigilance responsibilities

Local Principal Investigator (or nominated individual in PI's absence):

- Medical judgement in assigning seriousness and causality to SAEs.
- To fax SAE forms to BCTU within 24 hours of becoming aware, and to provide further follow-up information as soon as available.
- To report SAEs to the trust if required, in line with local arrangements.
- To sign an Investigator's Agreement accepting these responsibilities.

Chief Investigator (or nominated individual in CI's absence):

To assign causality and expected nature of SAEs.

To review all events assessed as SAEs in the opinion of the local investigator.

Birmingham Clinical Trials Unit:

- To prepare annual safety reports to main REC and TSC.
- To prepare SAE safety reports for the DMEC at 12-monthly intervals.
- To report all fatal SAEs to the DMEC for continuous safety review

Trial Steering Committee (TSC):

- To provide independent supervision of the scientific and ethical conduct of the trial on behalf of the Trial Sponsor and funding bodies.
- To review data, patient compliance, completion rates, adverse events (during treatment and up to end of follow-up).
- To receive and consider any recommendations from the DMEC on protocol modifications.

Data Monitoring & Ethics Committee (DMEC):

- To review overall safety and morbidity data to identify safety issues which may not be apparent on an individual case basis
- To recommend to the TSC whether the trial should continue unchanged, continue with protocol modifications, or stop.

6.6. Notification of Serious Breaches of GCP and/or the protocol

A "serious breach" is a breach which is likely to effect to a significant degree:

- (a) the safety or physical or mental integrity of the participants of the trial; or
- (b) the scientific value of the trial.

The BCTU on behalf of the Sponsor shall notify the REC in writing of any serious breach of:

- (a) the conditions and principles of GCP in connection with the trial; or
- (b) the protocol relating to the trial, as amended from time to time, within 7 days of becoming aware of that breach.

The Sponsor will be notified immediately of any case where the above definition applies during the trial conduct phase.

7. FOLLOW-UP

Trial data will be recorded by hospital research staff on the paper Case Report Forms (CRFs) and submitted to the ElaTION Trial Office at the BCTU.

It will be the responsibility of the investigator to ensure the accuracy of all data entered in the CRFs.

The ELaTION Delegation & Signature Log will identify all those personnel with responsibilities for data collection.

CRF versions may be amended by the ELaTION Trial Office, as appropriate, throughout the duration of the trial. Whilst this will not constitute a protocol amendment, new versions of the CRFs must be implemented by participating sites immediately on receipt.

7.1. Follow-up assessments

Follow-up will be undertaken for 1 year from randomisation or until definitive diagnosis has been obtained if not achieved during that first year. This will be sufficient time to allow for further FNACs if required after the first test. Also this allows sufficient time for any surgery to be undertaken and histological diagnosis to be available.

For both intervention and control arms, diagnosis and management will proceed as follows:

Thy1 - repeat FNAC, especially if suspicion of malignancy. If Thy1 on three FNACs, then the recommendation is made for diagnostic surgery.

Thy 2 - repeat FNAC within 3-6 months. If two benign (Thy2) FNAC results are obtained then patient can be discharged. Consideration for discharge with a U2 scan and one Thy2 is allowed, but is not recommended for the purposes of this study.

Thy 3a - repeat FNAC within 3-6 months or discussion with MDT. Surgery may then be advised

Thy3/3f/4/5 - surgery is necessary.

All repeat FNAC must be undertaken using the same ultrasound technique as the first one specified by the randomisation and ideally by the same RTE-accredited radiologist.

All follow-up data will be captured on the relevant CRF and returned to the ElaTION Trial Office.

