7.7. Definition of the End of Trial

The end of the trial will be 6 months after the last data capture, i.e. 6 months after the date of the last visit of the last patient undergoing protocol based treatment. Within ElaTION, the last visit is once the last participant has reached 1 year follow-up.

However, patients will be asked for permission to monitor long-term survival and recurrence rates through medical interventions, HES, ONS, cancer and other registry data and GP information.

The Trials Office will notify the REC the trial has ended and a summary of the clinical trial report will be provided within 12 months of the end of trial.

A copy of the end of trial notification as well as the summary report is also sent to the University of Birmingham Research Governance Team at the time these are sent to the REC.

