8.1.2 Secondary Outcome Measures

The secondary outcome measures for the study are:

- 1. Number of FNACs needed to obtain a definitive diagnosis in each patient;
- 2. Time from first FNAC to obtaining a definitive diagnosis in each arm;
- 3. The proportion of patients with a benign histology, compared between arms;
- 4. The proportion of patients who have a non-diagnostic (Thy 1) cytology result following any FNAC by arm;
- 5. The proportion of patients who receive surgery by arm;
- 6. Accuracy of 1st FNAC results and repeated FNAC results, compared between arms;
- 7. If RTE or US without FNAC is as accurate as RTE or US with FNAC, compared between arms;
- 8. Patient reported anxiety, pain and quality of life(by the HADS questionnaire, VAPS and EQ-5D) at baseline and at 3, 6 and 12 months post-randomisation;
- 9. Radiologist survey-completed by radiologists at the end of the procedure to identify whether radiologists found RTE had contributed to their decisions, ease of use, and their prediction of malignancy of the nodule using RTE or US features alone;
- 10. Complication rate from any thyroidectomy at 30-days and 6 months post-surgery haematoma rate and temporary hypocalcaemia at 30 days and vocal cord palsy and permanent hypocalcaemia rate at 6 months.
- 11. Resource usage for consultation time and diagnostic testing procedures and subsequent management including consultations and surgical treatments.

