8.4.2 Secondary Outcome Analyses

The secondary outcome measures include a comparison of proportions between the RTE-FNAC and US-FNAC arms. These include:

- the non-diagnostic cytology (Thy 1) rate for any FNAC undertaken in each patient;
- the number of patients out of all randomised who have surgery but have a benign histology;
- the number of FNACs required to obtain a definitive diagnosis;
- the number of patients who had a benign (Thy 2) result following first FNAC and how this compares with subsequent FNAC results in accuracy;

- the number of patients who had a benign (U2) result on US scan and how this compares with subsequent FNAC results in accuracy
- and the complication rate following any thyroidectomy out of those who had surgery.

These will all be compared between the arms using a generalised linear mixed model and adjusting for the minimisation variables. A chi-squared or Fisher's exact text (as appropriate) will be performed as secondary analyses.

The number of overall FNACs required to reach a definitive diagnosis will be compared between the RTE and US arm using a chi-squared test for trend.

Time to diagnosis will be compared between arms using a log-rank test.

Sensitivities and specificities can be calculated following US-only and RTE-only guided protocols and US-guided FNAC and presented along with 95% confidence intervals using binomial exact methods. Comparisons will be made within each arm between the tests using McNemar's test. Continuous measurements taken over time (e.g. HADS) will be analysed using .

A more detailed description of all analyses can be found in the ElaTION Statistical Analysis Plan.

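### Section 7.7 closes visits before the follow-up promised in section 7.1 is complete, so late recruits still in the diagnostic pathway can lose secondary-outcome events

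*Protocol*

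**What the plan says.** Protocol section 7.1 sets the follow-up rule for each patient: "Follow-up will be undertaken for 1 year from randomisation or until definitive diagnosis has been obtained if not achieved during that first year". It gives no upper limit. It then says of this arrangement: "Also this allows sufficient time for any surgery to be undertaken and histological diagnosis to be available".

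Section 7.7 sets the calendar end. "The end of the trial will be 6 months after the last data capture", and the last visit is fixed as follows: "Within ElaTION, the last visit is once the last participant has reached 1 year follow-up". Patients without a diagnosis at that point are not mentioned.

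Sections 7.3 and 7.4 require complications to be recorded at 30 days and at 6 months after any thyroid operation.

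The outcomes that depend on complete follow-up are in sections 8.1.2 and 8.4.2. Surgery is "The proportion of patients who receive surgery by arm". Benign histology is "the number of patients out of all randomised who have surgery but have a benign histology". The proportion with a Thy1 result at any FNAC and the complication rate are also listed. On the comparisons listed in 8.4.2 the plan says: "These will all be compared between the arms using a generalised linear mixed model and adjusting for the minimisation variables", with a chi-squared or Fisher's exact test as a secondary analysis. The surgery proportion is not itemised in 8.4.2, but that list is introduced as a set of examples, so I take it to be analysed in the same way. Time to diagnosis is compared by a log-rank test.

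**The concern.** The two sections give sites different instructions for the same patient. Someone recruited near the end and still undiagnosed at month 12 must be followed further under 7.1, yet under 7.7 the last visit has passed. An analysis plan can choose how to count events. It cannot decide which follow-up rule sites apply, or recover data that were never collected.

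If 7.7 prevails, the patients cut off are those whose pathway is unfinished. Their later FNACs, surgery, histology and complications go unrecorded, and a simple proportion counts them as having had no event. Randomisation balances recruitment date between the arms, but it does not balance time to diagnosis. Whether RTE shortens that time is itself a secondary objective (section 2.2). If the arms differ in it, the slower arm loses more events, and the contrasts in surgery and benign histology are distorted.

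**Working it through.** **1. The plan's own figure.** Section 8.2 gives 10% versus 4% Thy1, 5% significance (two-sided reproduces it), 90% power, a continuity correction and 15% drop-out.
- Uncorrected: n = [1.960 x sqrt(2 x 0.07 x 0.93) + 1.282 x sqrt(0.10 x 0.90 + 0.04 x 0.96)]^2 / 0.06^2 = 378 per arm.
- Corrected: (n/4) x [1 + sqrt(1 + 4/(n x 0.06))]^2 = 411 per arm, 822 in total.
- Drop-out: 411/0.85 = 483.5, rounded up to 484 per arm, 968 in total.

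This reproduces exactly. It rests on the first FNAC only, so nothing below changes it.

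**2. Can a patient still be in the pathway at month 12?** Section 7.1 allows 3-6 months before the repeat FNAC after a Thy2. For Thy3a it says: "Thy 3a - repeat FNAC within 3-6 months or discussion with MDT. Surgery may then be advised". A patient with Thy2, then Thy3a, then a second repeat uses 3 + 3 = 6 to 6 + 6 = 12 months before any decision on surgery. At the long end the operation and histology fall after month 12. The protocol's own intervals therefore produce such patients, though it does not say how many.

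**3. Post-operative assessments.** An operation at month s after randomisation has its 6-month assessment at month s + 6. For the last recruit this falls after the 7.7 close whenever s + 6 > 12, that is, s > 6. More generally, it is lost for patients recruited within s - 6 months of the last recruit. This applies even to a patient whose histology was available within the year.

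**4. How many undiagnosed patients are exposed?** Only those still undiagnosed at close lose pathway events. Assumptions, none of them in the protocol: 5-10% undiagnosed at 12 months, late diagnoses taking up to 6 further months, and uniform accrual over 30 months. Section 8.3 gives 30 months as a centre average, not as the trial's accrual period.
- Undiagnosed at 12 months: 968 x 0.05 = 48 to 968 x 0.10 = 97.
- Share recruited in the last 6 months: 6/30 = 0.20.
- Exposed, at most: 48.4 x 0.20 = 9.7 to 96.8 x 0.20 = 19.4, so about 10 to 19 over both arms.
- With 42 months of accrual the share is 6/42 = 0.143, giving about 7 to 14.

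**5. Illustrative effect on the between-arm contrast.** Suppose a proportion u is undiagnosed at 12 months, half of late diagnoses are reached by surgery, and late diagnosis has constant hazard h. With uniform accrual over R months, the proportion of patients whose surgery is missed at the 7.7 close is 0.5 x u x (1 - exp(-hR))/(hR).
- Mild case: u = 5% control and 3% RTE, h unchanged from the first year (-ln(u)/12), R = 30. Missed: 0.33% and 0.17%, a spurious difference of about 0.2 percentage points.
- Severe case: u = 20% and 10%, half of those remaining diagnosed per further year (h = ln 2/12), R = 30. Missed: 0.5 x 0.20 x 0.475 = 4.75% and 0.5 x 0.10 x 0.475 = 2.38%, a difference of about 2.4 points.
- With R = 42 the range is about 0.1 to 1.9 points.

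In each case surgery is understated in the slower arm.

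**6. The same cases under a 12-month count for everyone.** Missed surgery is 0.5 x u: 2.5% and 1.5% in the mild case, 10% and 5% in the severe case. The differences are 1.0 and 5.0 points, larger than under the 7.7 close.

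**The case against.** The strongest reply is that this is a one-line wording matter. Section 7.7 also refers to the last patient undergoing protocol-based treatment, which could be read as waiting for undiagnosed patients. The 6 months before the end of trial might absorb stragglers, and consent is sought for registry and hospital-episode data. The primary outcome is untouched, the log-rank test handles administrative censoring, and the analysis plan, which is not shown, may fix a window.

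Much of this stands: the primary analysis, the sample size and time to diagnosis are safe, and the absence of an analysis window from the protocol is no defect in itself. The rest does not resolve the conflict. The next sentence of 7.7 fixes the last visit at 1 year, the 6 months begin only after data capture has ended, and the registry data are sought for survival and recurrence.

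A reader might also infer stronger points that the protocol does not support:
- **That following only undiagnosed patients beyond month 12 inflates surgery in the slower arm.** Under section 8.1 a diagnosed patient has two Thy2 results, one Thy2 with a U2 scan, or histology, so further diagnostic surgery is not expected. A late operation in an undiagnosed patient is a real consequence of the pathway. Surgery after month 12 in someone already classed as benign could go uncounted, but that is a marginal leak.
- **That section 7.1 wrongly claims 1 year is enough.** The claim follows the whole rule, including the extension.
- **That all 48 to 97 patients assumed undiagnosed at month 12 are affected, or that follow-up runs from 12 to 42 months.** Only those still undiagnosed at close are cut off, and 42 months would treat a centre-average recruitment period as the trial's.

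**Conclusion.** The contradiction is real, and an analysis plan cannot remove it. Applied as written, 7.7 cuts off late recruits who are still undiagnosed or still awaiting a 6-month post-operative assessment. Surgery, benign histology and any-Thy1 would be under-counted, more so in whichever arm reaches diagnosis more slowly, and the comparisons as described make no allowance for unequal follow-up. If time to diagnosis is the same in both arms, events are still lost but no systematic difference between arms follows.

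The effect is probably modest: at most about 10 to 19 undiagnosed patients exposed under the assumptions in step 4, which exclude diagnosed patients who lose only a post-operative assessment. The 0.2 to 2.4 points in step 5 illustrate the mechanism under wider assumptions and are not an estimate, because the protocol does not give the share undiagnosed at 1 year. The matter is worth correcting because it is cheap and because the lost data cannot be recovered by analysis.

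**What to change.** - In section 7.7, define each patient's last visit as the later of 12 months from randomisation or definitive diagnosis, together with any post-operative assessment still due, up to a stated calendar cut-off. Word section 7.1 to match. The cut-off is needed because 7.1 has no upper limit and some patients may never meet the definition of diagnosis.
- For patients still undiagnosed at the cut-off, analyse surgery and benign histology by cumulative incidence with that date as the censoring date, at least as a sensitivity analysis to the planned comparison of proportions.
- Do not make a count truncated at 12 months the main comparison. It would apply to every patient the cut that 7.7 imposes only on late recruits, and it could make delayed surgery look like avoided surgery. It would also no longer measure the number of FNACs needed for a definitive diagnosis. Report it only as supplementary.

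The cost is wording in 7.1, 7.7 and 8.4.2, plus data capture running perhaps a few months longer for a small number of late recruits. The sample size does not change.
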